3.3.3.2 For calculating durations of treatments, adverse events (AEs), and medications

The followings rules will be applied for partial or missing start dates:

- If the day is missing, the 15th day of the given month will be used unless the month and year are the same as the month and year of enrollment, in which case the date of enrollment will be used.
- If the day and month are missing, the 1st of July will be used unless the year is the same as the year of enrollment, in which case the date of enrollment will be used.
- If the whole date is missing, the date of enrollment will be used.

The followings rules will be applied for partial or missing end dates:

- If the day is missing, the 15th day of the given month will be used unless:
 - the month and year are the same as the month and year of date of last contact, in which case the date of last contact will be used.
 - the imputed date is earlier that the start date, in which case the start date will be used.
- If the day and month are missing, the 1st of July will be used unless:
 - the year is the same as the year of last contact, in which case the date of last contact will be used.
 - the imputed date is earlier that the start date, in which case the start date will be used.
- If the whole date is missing, the date of last contact will be used.

Under those circumstances where missing data components will make the imputation of missing values problematic for calculating relevant time intervals, decisions will be made on a case by case basis for the pertinent analysis.

No other dates will be imputed.

3.3.4 Study End Date for Individual Subject

Study end date for individual subject is defined as the date of his/her exit visit. Note that a subject who exits early from the study for whatever reasons will be invited to attend exit visit for data collection.

3.3.5 Other Conventions

Summary statistics (used interchangeably with the term “descriptive statistics”) for continuous data include sample size (N), mean, standard deviation (SD), median, minimum, and maximum. Categorical variables will be summarized using sample size (N), frequency and percentages of patients. In calculating the percentage, unless specified otherwise, the count of subjects “at risk” will be used as denominator. Ordinal variables will be handled as categorical variables in terms of presenting summary statistics.

Subject’s demographic and baseline characteristics, including height, weight, Fitzpatrick skin type and Allergan Jowl Fat Rating Scale (AJFRS) will be collected at Visit 1 (Screening) and the value at Visit 1 (Screening) will be used as baseline value. For efficacy parameters, such as Allergan Loss of Jawline Definition Scale (ALJDS), CR (Clinician-Reported) and PR (Patient reported) Submental Fat Rating Scale (SMFRS) scores, Submental Skin Laxity Grade (SMSLG) score, FACE-Q™ satisfaction with lower face and jawline score; FACE-Q™ appraisal of neck; and FACE-Q™ appraisal of area under chin, baseline value is defined as the assessment outcome taken at Visit 1 (Screening). [REDACTED]

[REDACTED].

Change from baseline is calculated as ‘visit value minus baseline value’. Percentage change from baseline is calculated as change from baseline divided by baseline value, then multiplied by 100. If baseline value is zero, percentage change from baseline will be undefined or not evaluable (NE). If baseline value is missing, percentage change from baseline will be missing.

Data will be pooled across clinical sites/centers for all analyses.

The International System of Units (Système international d'unités or SI) is the current international standard metric system. The SI units will be used for the reporting in all Tables/Figures/Listings for this study.

All statistical analysis and reporting will be performed using [REDACTED].

4. Subject Disposition and Exit Status

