3.2 BELKYRA® TREATMENT

Subjects will undergo treatment with BELKYRA® injected into subcutaneous fat tissue in the submental area (Visit 2.1/Day 0) (note: Screening and Visit 2.1/Day 0 may occur the same day if all eligibility criteria are confirmed prior to treatment and the subject is not participating in the Biopsy Sub-study). Seven days after the initial BELKYRA® treatment (Visit 3.1), the subject will return to the clinic for a safety evaluation. Eight weeks after BELKYRA® treatment, the submental profile will be evaluated by the Investigator and subject. If the Investigator and subject agree that no further intervention is required to achieve the desired result, subjects may receive VOLUMA™ treatment (Visit 4). If further intervention is required to achieve the desired result, subjects may receive up to 5 optional BELKYRA® treatments (Visits 2.2 to 2.6). Optional BELKYRA® treatments will be

Clinical Study Protocol: CMO-MA-FAS-0513

administered at least 8 weeks apart, for a maximum of 6 treatments (including initial BELKYRA® treatment at Visit 2.1/Day 0). Subjects who receive optional BELKYRA® treatments will be contacted by telephone 7 days after each treatment for safety evaluation (Visits 3.2 to 3.6). Eight weeks after each BELKYRA® treatment, the submental profile will be assessed, as described above, and a decision made whether further BELKYRA® treatments are desired. When it is determined that further BELKYRA® intervention is not required or the maximum number (6) of BELKYRA® treatments have been administered, the subject receives VOLUMA™ treatment (Visit 4).

NOTE: Subjects participating in the Biopsy Sub-study will have an additional visit (Visit B2) between the final BELKYRA® treatment and the first VOLUMA™ treatment. See *Figure 3.1* and *Section 3.1: Biopsy Sub-Study*.

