4.2 INCLUSION CRITERIA

The following are requirements for entry into the study.

1. Male and females 18 to 65 years of age inclusive on the day of initial BELKYRA® treatment
2. Sign the Independent Ethics Committee (IEC)/Institutional Review Board (IRB)-approved informed consent form (ICF) prior to any study-related procedures being performed
3. Grade 2 or above on the ALJDS [REDACTED]

Clinical Study Protocol: CMO-MA-FAS-0513

- 4. Submental fat graded by the Investigator as 2 or 3 using the Clinician-Rated Submental Fat Rating Scale (CR-SMFRS) [REDACTED]

- [REDACTED]
- [REDACTED]
- [REDACTED]
- [REDACTED]
- [REDACTED]
- [REDACTED]
- [REDACTED]
- [REDACTED]
- [REDACTED]
- [REDACTED]

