10 STATISTICAL METHODS

10.1 GENERAL STATISTICAL CONSIDERATIONS

General statistical analysis methods are provided below; full details will be provided in a separate Statistical Analysis Plan (SAP), which will be finalized prior to database lock.

Data will be summarized using descriptive statistics (number of observations (n), mean, standard deviation, median, minimum, and maximum for continuous variables; and n and percent for categorical variables). Confidence intervals (95%) will be provided for the efficacy endpoints.

Three critical time points, baseline (Visit 2.1/Day 0), Visit 4 (end of BELKYRA® treatment, prior to VOLUMA™ treatment), and end of study (Exit/Visit 6; end of VOLUMA™ treatment), will be referenced in most of statistical analyses for this study.

Baseline is defined as the latest assessment prior to any study treatments for each subject. End of study is the last clinical visit an enrolled subject has in this study. For subjects who complete this study, the end of study visit will be their Visit 6 visit; for subjects who drop out

Clinical Study Protocol: CMO-MA-FAS-0513

early, they will be asked to come back for the last clinical visit for end of study data collection.

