6.2.1 Primary Efficacy Analysis16

6.2.2 Secondary Efficacy Analyses16

[REDACTED]

6.3 SubGroup Analyses 19

7. Safety Analyses.....19

7.1 Exposure to Study Treatment(s)..... 19

7.2 Adverse Events 20

7.3 Serious Adverse Events 21

7.4 Other Safety Analysis..... 22

7.5 Pregnancy 22

7.6 Subgroup Analyses for Safety Variables 22

8. Pharmacokinetic, Biomarker, Genomic, or Immunogenicity Data Analyses
.....22

9. Health Outcomes Data Analyses22

10. Interim Analyses22

11. Data Collected but not Analyzed.....23

12. References.....23

13. Appendices24

Summary of Changes

Version Number	Version Date	Author	Changes Made
1.0	14-Jan-2019	[REDACTED]	Initial Version
2.0	29-Aug-2019	[REDACTED]	Changes from V1.0 to V2.0 include: 
 • Revisions to section 6.2.3.3 - Image Analysis • Revisions to section 7.4 - Other Safety Analysis • [REDACTED]
3.0	21-Feb2020	[REDACTED]	Changes from V2.0 to V3.0 include: 
 • Addition of section 6.3 - SubGroup Analyses • [REDACTED]

1. Introduction

The purpose of this Statistical Analysis Plan (SAP) is to provide details of the data analyses as outlined in the study protocol dated on March 21, 2018 and titled “A Prospective, Open-label Study to Evaluate Sequential Treatment with BELKYRA® and Juvéderm® VOLUMA with Lidocaine (VOLUMA) for Overall Improvement in Jawline Contour”.

This SAP should be reviewed in conjunction with the study protocol. In case of any discrepancies in the statistics section between the protocol and the SAP, the SAP will supersede the protocol, as the SAP is intended to be more precise and specific. Any amendment to the SAP will be made prior to database lock. Any additional analyses performed but not described in the final SAP or deviations from the final SAP will be documented in the clinical study report.

This study is a Phase IV, post-marketing study sponsored by Allergan. It is a prospective, open-label, multi-center, interventional, drug and medical device study to evaluate the combined effectiveness of sequential BELKYRA treatments of convexity or fullness associated with submental fat and VOLUMA to restore volume along the mandible in enhancing the overall contour of the jawline. This post-marketing study includes an exploratory endpoint for a Biopsy Sub-study to evaluate histological changes from baseline to after the final BELKYRA treatment.

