2.1 Study Design

This Phase IV trial is a prospective, open-label, multi-center, interventional, drug and medical device, post-marketing study. Each subject will act as his/her own control. Subjects will attend a minimum of 6 and maximum of 18 visits.

Approximately 50 male and female subjects will be treated. Approximately 10 of them are expected to participate in the Biopsy Sub-study.

All subjects will sign an informed consent form (ICF) at the Screening Visit (Visit 1). Eligible subjects will undergo treatment with BELKYRA injected into subcutaneous pre-platysma fat tissue in the submental area (Visit 2.1/Day 0). Seven days after the initial BELKYRA treatment (Visit 3.1), the subject will return to the clinic for a safety evaluation. Eight weeks after BELKYRA treatment, the submental profile will be evaluated by the investigator and the subject. If further BELKYRA intervention is required to achieve the desired result, subjects may receive up to 5 optional BELKYRA treatments (Visits 2.2 to 2.6), for a maximum of 6 treatments including the initial required treatment. Subjects who receive optional BELKYRA treatments will be contacted by telephone 7 days after treatment for safety evaluation (Visits 3.2 to 3.6). The submental profile will be assessed as described 8 weeks after each BELKYRA treatment, and a decision made if further BELKYRA treatments are desired.

When the investigator and the subject agree that no further BELKYRA intervention is required to achieve the desired result, the subject may receive VOLUMA treatment (Visit 4). Fourteen days after VOLUMA treatment, subjects will return to the clinic (Visit 5) and the investigator will assess whether a VOLUMA touch up treatment is to be performed. All subjects will attend a final exit visit (Visit 6) which is 4 weeks after the last VOLUMA treatment (Visit 4 if no touch-up done or Visit 5, if touch-up was performed).

Subjects will have the option of participating in a Biopsy Sub-study. Participation in the sub-study is voluntary and will not affect the subject's eligibility to participate in the main study. Biopsy samples will be collected from the submental region at 2 time points: Visit B1 will occur at least 4 weeks before the first BELKYRA treatment (at Visit 2.1); Visit B2 will occur 8 weeks after the last BELKYRA treatment and at least 4 weeks prior to VOLUMA treatment (at Visit 4). Histological changes from baseline to after final BELKYRA treatment(s) will be evaluated.

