5.4 Medical History

Descriptions of medical history findings will be coded using latest Medical Dictionary for Regulatory Activities (MedDRA). Medical history will be summarized for the safety population by the number and percentage of patients within each system organ class (SOC) and PT, sorted descending by overall frequency.

Medical history will be listed for all patients in the safety population. Medical history data listings will be sorted by patient number, start date, SOC, PT and verbatim term.

6. Efficacy Analyses

For this post-marketing study, efficacy data are collected at three critical time points, namely, Baseline (prior to Visit 2.1/Day 0), Visit 4 (end of BELKYRA treatment, prior to VOLUMA treatment), and final study visit (Exit Visit 6; end of VOLUMA treatment). The three critical time points will be referenced in most of the statistical analyses for this study. [REDACTED]

Efficacy analyses will be conducted to evaluate the combined effectiveness of sequential treatments with BELKYRA and Juvéderm VOLUMA on the following parameters: Allergan Loss of Jawline Definition Scale (ALJDS), CR (Clinician-Reported) and PR (Patient reported) Submental Fat Rating Scale (SMFRS) scores, Submental Skin Laxity Grade (SMSLG) score, FACE-Q™ satisfaction with lower face and jawline score; FACE-Q™ appraisal of neck; and FACE-Q™ appraisal of area under chin, and investigator and subject [REDACTED]

Efficacy analyses to evaluate the effect of BELKYRA treatment will be conducted at

- Visit 4 (after last BELKYRA treatment) from baseline on ALJDS score, SMSLG score, FACE-Q™ satisfaction with lower face and jawline score; FACE-Q™ appraisal of neck score; FACE-Q™ appraisal of area under chin score.
- Visit 2.x (after each treatment of BELKYRA) from baseline on CR and PR SMFRS scores;
- Visit B2 (after the last BELKYRA treatment) from Visit B1 (before the first BELKYRA treatment) for histological changes in the submental tissue

[REDACTED]

All efficacy analyses will be based on the evaluable population (for combined effectiveness assessments); and on the full analysis population (for BELKYRA treatment evaluation).

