6.1 Collection of Efficacy Measurements and Derivation of Efficacy Variables

The following measurements and variables are of the efficacy interests. Data on Submental convexity or fullness and Jawline contour assessments, including ALJDS (investigator and independent reviewer), CR-SMFRS, PR-SMFRS, SMSLG and FACE-Q™ Satisfaction with lower face and jawline score/Appraisal of Neck/Appraisal of Area under Chin are collected at baseline (Visit 2.1/Day 0), Visit 4 (end of BELKYRA treatment, prior to VOLUMA treatment), and final study visit (Visit 6; end of VOLUMA treatment). [REDACTED]

- [REDACTED].
- Measurement: ALJDS by investigator and by independent reviewer;
Variables: Change on ALJDS from baseline (numeric variable on the value of right side; and value of left side); and having had at least 1-point improvement from baseline (binary variable). Improvement is defined as having had negative change from baseline.
 - Measurement: CR-SMFRS;
Variables: Change on CR-SMFRS from baseline (numeric variable). Improvement is defined as having had negative change from baseline.
 - Measurement: PR-SMFRS;
Variables: Change on PR-SMFRS from baseline (numeric variable). Improvement is defined as having had negative change from baseline.
 - Measurement: SMSLG;
Variables: Change on SMSLG from baseline (numeric variable). Improvement is defined as having had negative change from baseline.

Statistical Analysis Plan

- Measurement: FACE-Q™ lower face and jawline;
Variables: Change on FACE-Q™ lower face and jawline from baseline (numeric variable on combined scores). Improvement is defined as having had positive change from baseline.
- Measurement: FACE-Q™ Neck;
Variables: Change on FACE-Q™ Neck from baseline (numeric variable on combined scores). Improvement is defined as having had positive change from baseline.
- Measurement: FACE-Q™ Chin;
Variables: Change on FACE-Q™ Chin from baseline (numeric variable on combined scores). Improvement is defined as having had positive change from baseline.

█ [REDACTED]

█ [REDACTED]

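### The SAP takes the ALJDS baseline from Screening in one section and from Day 0 in another, so the reference value for the single-arm primary responder rate is not fixed

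*SAP*

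**What the plan says.** - SAP 3.3.5 lists the efficacy scales, ALJDS among them, and says their "baseline value is defined as the assessment outcome taken at Visit 1 (Screening"). Redacted text follows that sentence.
- The opening of SAP 6 names the first critical time point as "Baseline (prior to Visit 2.1/Day 0"), without a visit.
- SAP 6.1 says the same scales, with ALJDS rated by both the Investigator and the Independent Reviewer, "are collected at baseline (Visit 2.1/Day 0), Visit 4 (end of BELKYRA treatment, prior to VOLUMA treatment), and final study visit".
- Protocol 10.1 labels baseline as Visit 2.1/Day 0 and then states: "Baseline is defined as the latest assessment prior to any study treatments for each subject".
- SAP 6.2.1, the primary analysis, measures improvement from baseline and names no visit.
- On discrepancies in the statistics section, SAP 1 says "the SAP will supersede the protocol".
- Protocol 4.2 requires "Grade 2 or above on the ALJDS" for entry.
- On timing, Protocol 3.2 notes that "Screening and Visit 2.1/Day 0 may occur the same day if all eligibility criteria are confirmed prior to treatment", and only for subjects outside the Biopsy Sub-study. For those in it, SAP 2.1 says "Visit B1 will occur at least 4 weeks before the first BELKYRA treatment (at Visit 2.1").

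**The concern.** The study is open-label with one arm, so the reference rating carries the whole primary result. Two programmers working from SAP 3.3.5 and SAP 6.1 could pick different ratings and classify the same subject differently.

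The choice may also push the result one way. Entry is restricted to subjects rated 2 or worse on the scale that defines response. The rating used for that selection is probably the Screening one. Subjects whose Screening rating happened to err upward are then over-represented, and some will appear to improve at exit with no real change. A later pre-treatment rating that was not used for selection would be less affected.

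This inflation argument applies to ALJDS. For the other scales listed in SAP 3.3.5, only the contradiction is claimed. The primary analysis is a rate with an exact confidence interval, so the estimate is at stake and not a test decision.

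**Working it through.** **1. The plan's own precision figure.** Inputs from Protocol 10.7: n = 40, p = 0.78, stated half-width 14.0%, drop-out 20%.
- Wald: 1.96 × √(0.78 × 0.22 / 40) = 12.8 points. With continuity correction, add 1/(2 × 40) = 1.25, giving 14.1 points.
- Exact (Clopper-Pearson): half-width 13.7 points at 31.2 responders and 13.8 at 31.
- Enrolment: 40 / (1 − 0.20) = 50.

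The stated 14.0 lies between the exact and continuity-corrected values, and the 50 is reproduced. Neither depends on the baseline visit, so the sample size is not in question.

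**2. Weight of one subject.** At n = 40, one changed classification moves the rate by 1/40 = 2.5 points. Starting from 31/40 = 77.5% (exact 95% CI 61.5 to 89.2), one subject either way gives 75.0% or 80.0%, and four give 67.5% or 87.5%.

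**3. Whether the definitions can differ.** SAP 6 is compatible with either visit. SAP 3.3.5 and SAP 6.1 are not compatible unless the two visits fall on one day. The precedence rule ranks SAP 3.3.5 above Protocol 10.1 but does not rank it against SAP 6.1. Same-day visits are optional for most subjects and excluded for biopsy subjects. In those subjects Visit B1 can be no earlier than Screening (Protocol 7.1.7) and precedes Day 0 by 4 weeks or more.

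**4. Whether two ratings exist.** This is supported but not proven. SAP 6.1 puts ALJDS collection at Day 0. Images are taken before each study treatment (Protocol 7.1.6, SAP 6.2.3.3), and Protocol 7.2.1 ties images to the live ratings. Table 1.1 and the visit procedures are not visible.

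**5. Possible size of the inflation.** The documents give no rating-agreement data for ALJDS, so every input here is assumed except the entry cut-off of 2, the planned 78% and the 10 of 50.
- Latent severity: mean 1.5, 2.0 or 2.5; SD 0.8 or 1.0.
- Rating error: SD 0.3, 0.45 or 0.6; correlation between Screening and Day 0 errors 0, 0.5 or 0.8; exit error independent.
- Rating = round(latent + error), limited to 0–4; one rating per subject, sides not modelled.
- Selection: Screening rating ≥ 2.
- Gap = P(exit ≤ Screening − 1) − P(exit ≤ Day 0 − 1).

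This makes 54 settings, each with 1,000,000 simulated subjects. Ranges among subjects with separate ratings:

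| Error correlation | Gap, no true change (points) | Gap when Day 0-based rate is 78% (points) | Screening-based rate then reads | Spurious responders on Day 0 baseline, no true change |
|---|---|---|---|---|
| 0 | 1.8–14.0 | 3.0–12.5 | 81–91% | 15–29% |
| 0.5 | 1.2–8.5 | 2.0–8.3 | 80–86% | 16–34% |
| 0.8 | 0.7–5.0 | 1.3–5.1 | 79–83% | 17–38% |

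If only the biopsy subjects have separate ratings, the share is 10/50 = 0.2. The trial-level excess is then 0.2 × 0.7 = 0.1 to 0.2 × 14.0 = 2.8 points with no true change, and 0.2 × 1.3 = 0.3 to 0.2 × 12.5 = 2.5 points at 78%. If grade ≥ 2 is required at both ratings, the gap is zero within simulation noise (±0.11 points).

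**The case against.** SAP 3.3.5 is the only SAP sentence that defines the baseline value, and it names ALJDS. SAP 6.1 mentions Day 0 in brackets while describing data collection, so a programmer would normally follow 3.3.5. SAP 6.1 also lists one baseline, not a Screening and a Day 0 rating. If ALJDS was rated once before treatment, at Screening, that rating is also the latest pre-treatment one, and 3.3.5 agrees in effect with the Protocol 10.1 definition. The photograph argument is weak: images are also taken before the repeat BELKYRA treatments, where SAP 6 lists no ALJDS evaluation. Redacted text after the sentence in 3.3.5, or the unseen visit schedule, could resolve the matter. The inflation figures rest on assumptions. In the scenario closest to the documents they come to about one subject in 40 (2.8% × 40 = 1.1), against a planned half-width of 14.0 points. A Day 0 baseline leaves most of the regression to the mean in place. Amending the bracket in 6.1 would also end the conflict.

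Most of this stands as a limit on size: the gap may be small or zero, and confidence belongs to the contradiction, not to the inflation figures. It does not remove the contradiction. The visible sentences in 3.3.5 and 6.1 name different visits for the same scale, and 3.3.5 departs from the protocol with no visible reason. Settling on Screening would make the text consistent, but it would keep the likely selection rating as the reference.

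**Conclusion.** The concern holds. The SAP does not fix one baseline for the primary endpoint, and its explicit definition departs from the protocol's. This is certain on the visible text, subject to whatever the redactions contain.

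The numerical effect cannot be derived from the documents. It requires separate Screening and Day 0 ratings, and the upward bias also requires Screening to be the selection rating. Across the assumed settings, the excess in affected subjects is 0.7 to 14.0 points with no true change and 1.3 to 12.5 points at the planned 78%. At trial level it is at most about 2.8 points if only biopsy subjects are affected. It would be larger if other subjects also had separate visits, and zero if the ratings coincide. Changing the baseline does not cure regression to the mean: with no true change, 15–38% spurious responders remain on a Day 0 baseline under the same assumptions.

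**What to change.** In SAP 3.3.5, define the efficacy baseline as the last assessment before the first BELKYRA injection, using the Screening value only where no later one exists. This is the Protocol 10.1 rule. Bring the baseline wording in SAP 6 and 6.1 into line. Report the Screening-based ALJDS responder rate as a sensitivity analysis where both ratings exist, and state how many subjects have separate Screening and Day 0 ratings. Make the change before database lock, as SAP 1 requires of any SAP amendment.

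The cost is one sentence, two aligned passages and one extra summary. No new data are needed: any Day 0 ratings would be used, and otherwise the fallback keeps the Screening value. The responder rate may come out slightly less favourable.
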